7.3 Subject Population(s) for Analysis

All-completed population: Only subjects who completed ALL study related procedures and follow-up will be included

8 Safety and Adverse Events

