1.5 Risks and Benefits

C-11 choline is involved in phosphorylation process integrated into phospholipids in the cell membrane as part of phosphatidylcholine, which is vital in prostate cancer cell. The main risk involves the exposure to the radioactivity associated with the C-11 isotope incorporation. This exposure has been calculated to be much lower than the F-18 FDG. In addition, there is no radiation risk related to MR scan. For MR safety concern, each subject will undergo MR safety screening performed by PET/MR technologist prior to imaging.

2 Study Objectives

Primary Objective:

- 1) Test whether a hybrid combination of focused C-11 choline PET/MR and pelvic mpMRI on a PET/MR system is feasible

Secondary Objective(s):

- 1) Determine the efficacy (added values) of a hybrid combination of molecular focused C-11 choline PET/MR and functional and anatomic pelvic mpMRI in comparison with clinical findings.
- 2) Determine the efficacy (added values) of a torso C-11 choline PET/MR in comparison with conventional CT and bone scan in depicting metastasis to lymph node and bone.

3 Study Design

This study will be a prospective study to test and optimize the feasibility of hybrid 3T PET/MR scan in diagnosing and staging high and very high risk prostate cancer patients.

The FDA approved C-11 choline PET tracer at a dose of 12-14 mCi will be administered intravenously prior to fused PET/MR scan, and prior to diagnostic pelvic mpMRI scan while patient lying in the scanner.

In addition, single dose of Gadavist® (Gadobutrol, Bayer) is at no more than 0.1 mmol/kg will be administered intravenously for pelvic mpMRI.

The whole imaging procedure will be conducted on an FDA approved GE SIGNA 3T PET/MR scanner.

The C11-choline PET/MR and pelvic mpMRI findings and results will be compared with serum PSA level, Gleason score, clinical CT and nuclear medicine whole body bone scintigraphy findings, and histopathological results obtained through standard of care management.

Our primary interest is to investigate the feasibility of hybrid C11-Choline PET/MR fusion and pelvic mpMRI in imaging primary prostate cancer.

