3.1 General Description

It is possible that improved comprehensive imaging techniques may more accurately stage untreated patients with high risk prostate cancer as well as better characterize the intra-parenchymal tumor. It is of interest to focus on potential synergy between molecular focused C-11 choline PET and functional and anatomic pelvic mpMRI. Therefore, we wish to determine the feasibility and efficacy (added value) of a hybrid, combination of torso and focused C-11 choline PET/MR with pelvic mpMRI on a clinical 3T PET/MR system in characterizing and staging very high-risk and high-risk prostate cancer patients, which could provide a more accurate tumor characterization and staging information and lead to individualized precise treatment.

3.2 Number of Subjects:

A total of twenty subjects will complete the study. Additional candidates may be screened to ensure completion of twenty subjects.

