3.4 Primary Study Endpoints

Patient: Completion of all imaging examinations with laboratory results.

Data analysis:

Objective 1: Descriptive study. With biopsy and/or surgical histopathology as gold standard, the sensitivity, specificity and accuracy of PET/MR will be calculated.

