4.4 Early Withdrawal of Subject

If a subject cannot finish the PET/MR imaging due to claustrophobia, he will be withdrawn. After PET/MR imaging, if a subject declines to undergo clinical evaluation and standard care of imaging, he will be withdrawn.

We plan to recruit a replacement subject in the event that a subject withdraws early to maintain the target number of 10 subjects.

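### The only analysis set (7.3) is men who completed everything, so in this feasibility study the completion endpoint is 100% by construction

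*Combined protocol and SAP*

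**What the plan says.** Feasibility is the only primary objective in section 2, and section 3 repeats it: "Our primary interest is to investigate the feasibility of hybrid C11-Choline PET/MR fusion and pelvic mpMRI in imaging primary prostate cancer". The multiplicity paragraph in 7.2 also relies on there being one primary objective.

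Section 3.4 gives the patient-level primary endpoint as "Completion of all imaging examinations with laboratory results". The data-analysis text beneath it, for Objective 1, specifies something else: "With biopsy and/or surgical histopathology as gold standard, the sensitivity, specificity and accuracy of PET/MR will be calculated". No completion proportion, denominator or success threshold appears there or in 7.2. For the procedure itself, 7.2 plans descriptive summaries of total time, tolerance and satisfaction.

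Four provisions decide who is counted:

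- **4.4, during the scan:** "If a subject cannot finish the PET/MR imaging due to claustrophobia, he will be withdrawn".
- **4.4, after the scan:** "After PET/MR imaging, if a subject declines to undergo clinical evaluation and standard care of imaging, he will be withdrawn". Early withdrawals are replaced. Section 4.4.1 adds that a subject may be withdrawn for discomfort.
- **3.2:** "Additional candidates may be screened to ensure completion of twenty subjects".
- **7.3, the sole analysis population:** "Only subjects who completed ALL study related procedures and follow-up will be included".

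Section 4.4.2 keeps data collected up to withdrawal as part of the study and requires the Day 2 contact whatever the subject's status. Section 7.3 assigns those subjects to no analysis. The missing-data paragraph in 7.2 says only that no missing imaging data are expected.

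**The concern.** A feasibility study learns mainly from the men who could not go through with the procedure. Here the endpoint is completion, and the rule for entering the analysis is also completion. Once the set is conditioned on the endpoint, the endpoint cannot vary. Replacement until twenty finish also fixes the number of completers in advance, so only the count of failures carries information, and 7.3 leaves that count out.

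The result could not distinguish a procedure that every man finishes from one that several cannot. The tolerance and satisfaction summaries would be selected in the same direction, because a man who stopped for claustrophobia or discomfort is not in the set.

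A lesser consequence concerns the word follow-up in 7.3. It most likely means the Day 2 call, since 8.1 defines the follow-up period by that call, although 3.3 also lists clinical follow-up as a reference standard. On the first reading, a fully imaged man who misses the call drops out of the imaging comparisons.

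**Working it through.** **The plan's own figure.** No completion rate, precision or withdrawal rate is stated, so there is no feasibility figure to reproduce. The only calculated figure is the 82% McNemar power in 7.1 (n = 20, difference d = 0.30, discordant proportion ψ = 0.31, two-sided 0.05). The Miettinen approximation is Φ[(√n·d·√ψ − 1.96ψ) / √(ψ² − d²(3+ψ)/4)] = Φ[(0.747 − 0.608)/0.147] = 82.8%, which agrees. It concerns lymph-node accuracy and says nothing about completion.

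**Step 1: completion in the 7.3 set.** Completing all procedures implies completing all imaging. With c completers and f failures, 7.3 keeps the c and drops the f, so the proportion is c/c = 100% for every f. A confidence interval on that value has no meaning.

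**Step 2: completion with failures in the denominator.** c = 20 comes from 3.2. The values of f are assumptions. The exact (Clopper-Pearson) limits are the 2.5% point of Beta(20, f+1) and the 97.5% point of Beta(21, f). Because recruitment stops at the 20th completer, the sampling is inverse, and the upper limit then uses Beta(20, f). The lower limit is unchanged.

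| Failures f (assumed) | In 7.3 set | 20/(20+f) | Exact 95% CI | Inverse-sampling 95% CI |
|---|---|---|---|---|
| 1 | 100% | 20/21 = 95.2% | 76.2–99.9 | 76.2–99.9 |
| 2 | 100% | 20/22 = 90.9% | 70.8–98.9 | 70.8–98.8 |
| 5 | 100% | 20/25 = 80.0% | 59.3–93.2 | 59.3–92.9 |

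The stopping rule barely changes the interval, so the ordinary exact interval is adequate.

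**Step 3: how often the rule would matter.** Let p be the true completion probability among men who start, assumed constant, with independent subjects. No failure occurs before the 20th completer with probability p²⁰, so the chance that at least one is left out is 1 − p²⁰. The expected number left out is 20(1 − p)/p. The values of p are assumptions.

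| p (assumed) | 1 − p²⁰ | Expected failures left out |
|---|---|---|
| 0.98 | 33% | 0.4 |
| 0.95 | 64% | 1.1 |
| 0.90 | 88% | 2.2 |
| 0.80 | 99% | 5.0 |

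**Step 4: does another section supply the denominator?** Section 3.4 gives accuracy measures. Section 7.2 gives time, tolerance and satisfaction. Section 4.4.2 retains the data but plans no analysis of them. No enrolled, injected or scan-started population is defined anywhere.

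**The case against.** The strongest reply is that the plan never promises a completion proportion. The completion line in 3.4 could be read as marking when a subject counts as finished, in which case the root gap is an undefined feasibility measure and 7.3 only compounds it. It is true that the endpoint is not written as a rate. But the line stands under primary endpoints, and if it is only a milestone then feasibility has no completion measure at all, while the remaining summaries are still confined to men who coped. The same change is needed on either reading.

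Second, the failures are not lost, because 4.4.2 keeps their data. This stands: the missing denominator is a defect of the written plan, not of the data. It makes the repair cheap but does not make it unnecessary.

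Third, the effect may be small. Section 4.2 excludes men who cannot tolerate MRI, no go/no-go decision depends on completion, and about twenty men give a wide interval in any case: even 20/20 has an exact 95% interval of 83.2–100%. All of this is fair, and at 98% true completion the rule would change nothing in about two of three such studies. Even so, the protocol itself foresees failures, since it writes rules for claustrophobia and for replacement.

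Fourth, 4.4.1 says only that subjects *may* be withdrawn for discomfort. That is so, but a man with an incomplete scan is outside the 7.3 set whether or not he is formally withdrawn.

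Finally, the choice between enrolled men and scan starters as denominator is a judgement that the documents do not settle. Reporting both counts meets this.

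**Conclusion.** The concern holds and should be corrected before analysis. As written, 7.3 removes from the primary feasibility endpoint the very events that endpoint exists to count, and it selects the time, tolerance and satisfaction summaries in the same way. This is a wrong rule for the objective, not just missing detail.

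That completion is 100% within the 7.3 set follows from the text and needs no assumption. How far this departs from the truth cannot be known from the documents. The illustrations above rest on assumed failure counts and on assumed, constant completion probabilities with independent subjects.

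The damage is limited. Accuracy results remain interpretable for completers. No adverse-event rate is planned, and 8.2 requires all events to be recorded, so no planned safety estimate is distorted.

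**What to change.** **In 7.3,** add a feasibility set: all subjects who start the PET/MR session, including those withdrawn and replaced. This fits the objective in section 2, which concerns the hybrid acquisition. Report alongside it the number who consented but never started, for example after the Day 1 MR safety screen in 6.2.

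**In 3.4,** define the completion proportion in that set, with an exact 95% confidence interval and the reasons for non-completion. Count failure to finish the PET/MR separately from later refusal of standard-care imaging.

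**In 7.2,** summarise time, tolerance and satisfaction in the same set where collected, stating the number missing. For the paired comparisons, use all subjects imaged by both methods, without requiring the Day 2 call. Require a reference result only for sensitivity, specificity, predictive values and accuracy, and state that this number may be below the 20 assumed in 7.1.

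As a secondary matter, list the safety documentation of 3.6 for every subject injected. Separately, and not part of this point's weight, the replacement rule in 4.4 ("We plan to recruit a replacement subject in the event that a subject withdraws early to maintain the target number of 10 subjects") must be reconciled with the 20 in the study summary, 3.2, 7.1 and 7.2.

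**Cost.** This is mainly wording, with no new visits, because data up to withdrawal and the Day 2 contact are already kept under 4.4.2. The reason for stopping must be recorded on the CRF. Patient-reported outcomes are listed as CRF data in 3.7, but 6.4 gives no time point for tolerance or satisfaction, so early stoppers may have none unless asked at discharge or withdrawal. The downside is that reported completion may fall below 100%, and the number with a reference result may be below 20.

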While patient lying on scanner table, 444-518MBq (12-14ⁱ mCi) C-11 choline will be injected as a bolus through a catheter inserted into a large peripheral vein.

Scan Range:

- Routinely from upper thigh to vertex of head, otherwise specified

Scan direction for PET

- Inferior to superior
- Start imaging immediately after the injection of tracer and acquire images with 2–5 minutes per bed position (totally about 5-6 bed positions). The total scanning duration is around 25-30 minutes

MR attenuation correction:

- Simultaneous PET/MR imaging with PET emission data reconstructed in 3D time-of-flight mode at multiple bed positions. During each bed position, coronal Dixon fat/water sequence, in-phase, and out-phase images will be performed for MR segmented attenuation correction.
- Diagnostic quality axial LAVA-FLEX only was obtained simultaneously with PET emission imaging acquisition at each bed position.

Part 2: Hybrid Focused PET/MR and mpMRI of the Pelvis (simultaneous acquisition of pelvic PET/MR and mpMRI without and with IV gadolinium contrast)

MR contrast agent and medicine

- For a contrast-enhanced scan the technologist will load and connect a power injector for administration of contrast material via a peripheral venous access. The contrast material and dose are both determined by the radiologist subject to departmental policy.
- Typically a single dose of Gadavist® (gadobutrol, Bayer) is used for studies of the prostate gland at our institution. The target contrast dose is no more than 0.1 mmol/kg for subjects with eGFR of higher than 30 mL/minute/1.73 m². Those with a GFR of 30 or less will not be admissible to the study. Contrast material is administered at 3 ml/sec followed by a saline flush of 20 ml at 3 ml /sec.
- 1 mg of glucagon will be administered subcutaneously at the start of the scan as an anti-peristaltic. Glucagon will not be given if the patient has a history of DM.

The following multiparametric prostate MR protocol will be applied. Simultaneous PET emission image will also be acquired. The total mpMRI scan time is around 40-50 minutes.

- Multiparametric MRI of the pelvis technique utilizing an institutional clinical MRI protocol.

Sites	Image sequences
Pelvis	
	Axial T1-weighted LAVA-FLEX*
	Axial DWI
Prostate (high resolution with small FOV)	
	Sagittal T2 FRFSE
	Axial T2 FRFSE
	Axial FOCUS DWI
	Coronal T2 FRFSE
	Axial DCE
Pelvis	
	Post Gd ax LAVA-FLEX (water only, fat only)

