3.6 Primary Safety Endpoints

Since C-11 choline is an essential nutrient needed for physiologic process as an integrated part of cell membrane component, and the quantities actually administered are in the micromolar range, there are no expected adverse reactions due to the primary study drug. The primary safety endpoint would be documentation of either lack of reaction to C-11 choline injection or detailed description of any adverse reaction (rash, fever, hypotension, dyspnea, chest pain) and treatment measures undertaken.

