4.4.1 When and How to Withdraw Subjects

Subjects may be withdrawn from the study if consent is withdrawn, if they no longer satisfy enrollment criteria or if they are unable to continue participation due to discomfort.

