4.4.2 Data Collection and Follow-up for Withdrawn Subjects

The C-11 choline PET/MR data will be retained for potential future analysis. Data collected on study subjects up to the time of withdrawal will remain as part of the study in a secured database in order for the study to maintain scientific validity.

Regardless of enrollment status, subjects will be contacted to collect Day 2 follow up information. This information will be recorded in the case report form documentation.

5 Study Drug

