5.9.4 Return or Destruction of Study Drug

After injection of the C 11 choline the syringe will be assayed for residual radioactivity, to be used in calculation of the precise injected dose. The syringe will then disposed of in the radioactive container for 3-4 hours, about ten half-life durations of C11-Choline (C11-Choline half-life of 20 minutes).

6 Study Procedures

Patients who have completed or will complete diagnostic body CT scan and nuclear medicine bone scan as part of standard care will be recruited and consented for participation in the study

PET/MRI is preferably scheduled 6 weeks after prostate biopsy to minimize the effects of post biopsy hemorrhage.

6.1 Day 0

Informed consent discussion with subject by research coordinator. Consent form signed by subject. Medical records will be reviewed by study coordinator. Subject's eGFR will be determined. If current serum creatinine level is unavailable, labs will be obtained for review.

Subject will be reminded to drink 48 ounces of water the day prior to study procedures. On the morning of the procedure, subjects will be counseled to fast for four hours prior to the procedure and drink 24 ounces of water.

6.2 Day 1

The patient will be screened for MR safety prior to entering the scan room, which may include the use of ferromagnetic screening.

[figure not shown]
1. Vital signs (sitting blood pressure, heart rate, respiratory rate, temperature) are measured by the radiology nurse, who records the results on the source document.
2. Investigator MD or research coordinator to see patient, review vital signs and discuss study objectives, explain the imaging procedures, answer questions. MD will sign and date the source document.
3. Subject is brought to the PET/MR imaging suite. Total dose of 12-14 mCi C-11 choline is injected I.V.
4. Torso PET/MR fusion scan is completed. Imaging time 20-30 minutes.
5. Pelvic mpMRI with PET data of pelvis completed. Imaging time 40-45.
6. Following completion of imaging, subject will return to the relax room and vital signs (sitting blood pressure, heart rate, respiratory rate and temperature) will be re-checked by

the radiology nurse, with the study coordinator recording the data in the source documents.

7. Subject will be discharged.

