6.4 Schedule of Events

Study Activity	Day 0	Day 1	Day 2 (follow up)
Informed consent	X		
Medical records review. Confirm study inclusion criteria. Data recorded on source document.	X		
Subject eGFR determined. Labs obtained if Current serum creatinine is unavailable.	X		
Vital signs prior to and following imaging sessions recorded on source document (sitting blood pressure, respiratory rate, temperature, heart rate)		X	
Torso PET/MR fusion scan		X	
Pelvic mpMRI (SOC)		X	
Adverse event evaluation. Results recorded on source document.		X	
Follow-up call to collect adverse events. Result recorded on source document.			X

7 Statistical Plan

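### The only analysis population is completers and nothing exempts the primary safety endpoint, so injected non-completers can be left out of the safety summary

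*Combined protocol and SAP*

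**What the plan says.** Section 7.3 names a single population, the all-completed one: "Only subjects who completed ALL study related procedures and follow-up will be included". No safety or all-injected population is defined anywhere.

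Section 3.6 defines the safety endpoint: "The primary safety endpoint would be documentation of either lack of reaction to C-11 choline injection or detailed description of any adverse reaction". It lists rash, fever, hypotension, dyspnea and chest pain as examples and sets no condition that imaging be completed.

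Injection comes before scanning. The imaging technique under Section 3.3 says "Start imaging immediately after the injection of tracer", and Section 6.2 puts the injection at step 3 and the two scans at steps 4 and 5.

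Section 4.4 withdraws a subject who cannot finish because of claustrophobia, and one who has been scanned but then declines the standard clinical work-up. It plans a replacement for early withdrawals. Section 4.4.1 also allows withdrawal of subjects "if they are unable to continue participation due to discomfort".

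On collection, Section 4.4.2 keeps data gathered up to withdrawal and adds: "Regardless of enrollment status, subjects will be contacted to collect Day 2 follow up information". Section 6.4 schedules adverse event evaluation on Day 1, and Section 8.2 requires every adverse event in the study period to be recorded.

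On vital signs, Section 6.2 step 6 reads "Following completion of imaging, subject will return to the relax room and vital signs" are rechecked, whereas Section 6.4 has "Vital signs prior to and following imaging sessions recorded on source document".

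**The concern.** The safety endpoint is triggered by exposure, but the only stated analysis rule selects on completion. A reaction that ends the session is the kind of event Section 3.6 exists to document, and it also makes the subject a non-completer. Membership of the analysed set can therefore depend on the outcome being summarised. Because withdrawn subjects are replaced, the shortfall would not show in the number analysed.

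At stake is the reported safety result of a small study whose protocol expects no reactions to the tracer. In that setting, leaving out one subject can change the summary from one reaction to none. The same rule drops an injected subject who finishes the scans but misses the Day 2 call, since 7.3 requires follow-up as well as procedures.

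**Working it through.** The plan states no figure for the safety endpoint, so there is none to reproduce. Its one sample-size figure (Section 7.1, 82% power) concerns the lymph node comparison and does not enter here.

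**Step 1: who is exposed.** By Sections 3.3 and 6.2, anyone who stops during either scan has already been injected.

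**Step 2: who is excluded.** Formal withdrawal is not needed. An unfinished scan or a missed Day 2 call is enough to fail the rule in 7.3. Subjects scanned in full who later decline standard imaging are withdrawn under 4.4.

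**Step 3: what is collected and what is analysed.** Sections 4.4.2, 6.4 and 8.2 govern collection and retention and are not limited to completers. Only 7.3 says who is analysed, and it is limited to completers. No section says which denominator the 3.6 endpoint uses.

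**Step 4: size, on assumed counts.** The number of completers, 20, comes from the Study Summary and Sections 3.2 and 7.1. (Section 4.4 gives a target of 10, which conflicts with these.) Assume that k injected subjects stop because of a reaction, that each is replaced, and that none of the 20 completers reacts. The documents give no value for k.

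- Completer set: 0/20, whatever k is.
- All-injected set: k/(20 + k).
- Exact (Clopper-Pearson) 95% limits for x events in n: the lower limit is the 0.025 quantile of Beta(x, n − x + 1) and the upper limit is the 0.975 quantile of Beta(x + 1, n − x). For x = 0 the lower limit is 0 and the upper limit is 1 − 0.025^(1/n), so for n = 20 it is 1 − 0.025^(1/20) = 0.168.

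| k | Completer set (95% CI) | All injected (95% CI) |
|---|---|---|
| 1 | 0/20 = 0% (0 to 16.8%) | 1/21 = 4.8% (0.1 to 23.8%) |
| 2 | 0/20 = 0% (0 to 16.8%) | 2/22 = 9.1% (1.1 to 29.2%) |
| 3 | 0/20 = 0% (0 to 16.8%) | 3/23 = 13.0% (2.8 to 33.6%) |

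The direction depends on why subjects leave. If one subject leaves without a reaction and one completer reacts, the completer set gives 1/20 = 5.0% against 1/21 = 4.8%, slightly the other way. Understatement arises when leaving is linked to the reaction.

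**Step 5: vital signs.** Section 6.2 step 6 attaches the repeat measurement to completed imaging and has no line for a stopped session. The wording in 6.4 carries no completion condition, and a stopped session still has a time after it. The two sections can therefore be read differently for a subject who stops early. This matters because hypotension and fever are among the listed reactions, and the Day 2 call in 6.3 asks about symptoms only.

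**The case against.** The strongest reply is that no event is lost. The 3.6 endpoint is a subject-by-subject description with no rate, denominator or completion condition. Section 7.2 lists no adverse event rate, and safety is handled in Section 8. There, all events are recorded and followed, an adverse event leading to hospitalisation is documented and reported as serious (8.1), and each event is evaluated for reporting to the IRB and FDA (8.3). On this view 7.3 concerns the imaging analyses only.

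Much of this stands. A reader might infer from 7.3 that a reaction ending the scan goes uncaptured or drops out of the endpoint altogether. The documents do not support that, because Sections 4.4.2, 6.4 and 8 require it to be recorded, retained and assessed. A reader might also infer that the Day 2 call is the only safety contact for a withdrawn subject. Section 8.2 rules that out: it requires the team to ask about adverse events at every contact and to examine where appropriate, and the moment the scan stops is such a contact. It is also fair that the withdrawal clauses name claustrophobia and discomfort rather than an adverse reaction, and that the counts above are assumed.

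What does not stand is the limit placed on 7.3. It is the plan's only statement of who is analysed, it carries no restriction to imaging, and 3.6 is labelled a primary endpoint. Recording an event does not settle whether it enters the summary.

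**Conclusion.** The point holds as a conflict over the analysis denominator. Section 7.3, followed literally, excludes injected non-completers from the analysed safety summary, while Sections 3.6, 4.4.2 and 8.2 treat their safety data as part of the study. If the endpoint is summarised in the completer set, reactions can be understated. With one reaction-related stop and a replacement, the summary reads 0/20 (upper 95% limit 16.8%) instead of 1/21 = 4.8% (upper limit 23.8%).

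This rests on two assumptions: that 7.3 is applied to the safety endpoint as written, and that at least one injected subject stops because of a reaction. The plan specifies no reaction rate, so it would go too far to say that a planned estimate is biased. The intervals are wide and overlap, so the figures show what the rule does and not how large the effect is likely to be.

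The vital signs point is smaller. It is a difference in wording between 6.2 step 6 and 6.4, and 6.4 does not itself impose a completion condition.

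**What to change.** In Section 7.3, add a safety population: every subject who received any C-11 choline, whether or not imaging or the Day 2 call was completed. State that the 3.6 endpoint is summarised in that population, and keep the completer population for the paired imaging comparisons.

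Separately, reconcile Section 6.2 step 6 with Section 6.4 so that it is clear how post-injection vital signs are recorded when a session stops early. Section 6.4 needs no change.

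The cost is a few sentences of protocol text and one more summary column. Day 2 information on withdrawn subjects is already collected under 4.4.2. The reported safety result may be slightly less favourable.
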